## 5 STUDY ENROLLMENT AND WITHDRAWAL

### 5.1 Inclusion Criteria

#### 5.1.1 Stage 1 (Questionnaire Component) Inclusion Criteria

A practitioner must meet all of the following criteria:

- Is enrolled in the National Dental PBRN as limited or full network members;
- Has completed an Enrollment Questionnaire;
- Is licensed in the U.S. to treat patients, treats patients in the U.S. on a recurring basis and maintains an active practice address at which he or she can be contacted; and
- Performs non-implant restorative (i.e., crowns) procedures routinely in his/her practice as reported on the enrollment questionnaire.

#### 5.1.2 Stage 2 (Clinical Component) Inclusion Criteria

**Patients:** Patients will be recruited from within practitioners' patients. In order to be eligible to participate in this study, patients must meet all of the following criteria:

- Age  $\geq$  18 years old;
- In need of a single - unit crown on a single natural tooth (1 through 32) and willing to have only one crown prepared during the patient's study period; and
- Willing and able to provide informed consent for treatment and return for the crown insertion.

**Practitioner:** In order to be eligible to participate in this study, a practitioner must meet all of the following criteria:

- Is a "Full" participation level member of the National Dental PBRN or willing to change from "limited" to "Full";
- Viewed a National Dental PBRN orientation session or has attended at least one annual regional meeting of practitioners;
- Has completed Stage 1 of the study (clinical crown questionnaire);
- Is a dentist who is licensed in the U.S. to treat patients, treats patients in the U.S. on a recurring basis and maintains an active practice address at which he or she can be contacted;
- Completed all region specific IRB requirements, as needed;
- Performs at least seven crowns per month;
- Affirms that the practice will devote sufficient time to allow for all the study procedures; and
- Confirms the participation of his/her dental laboratory/laboratories. (Practitioners who use optical Scanners (e.g. CEREC) along with a commercial lab and/or in-office milling for either a portion of crown procedures or exclusively are eligible to participate.)

**Laboratories:** Laboratories will be recruited by practitioners. In order to participate, the laboratories must be:

- Willing to complete the assigned evaluations of the crown preparations and other technical aspects of the clinical work;
- Willing to communicate with RCs regarding study expectations, preferably, this communication will occur in English; and

- Willing and able to participate in training with the RC.

## 5.2 Exclusion Criteria

### 5.2.1 Stage 2 (Clinical Component) Exclusion Criteria

**Patients:** Patients meeting the following criteria will be excluded from the study:

- In need of a crown associated with a fixed bridge or supported by a dental implant, without a need for a single-unit crown on a natural tooth.

## 5.3 Strategies for Recruitment and Retention

### 5.3.1 Stage 1 (Questionnaire Component)

Eligible dentists for the Stage 1 questionnaire will be identified based on the criteria noted from their responses on the Enrollment Questionnaire. All eligible dentists will first receive a study invitation email from the CC on behalf of the RC inviting them to participate in the study. The invitation will include a link to the electronic version of the questionnaire. Dentists will have an opportunity to complete an electronic or paper version of the questionnaire in order to increase participation rates. Based on previous regional PBRN questionnaire studies, we anticipate a response rate of approximately 60-70%. Calls will be held as needed with the RCs to review contact information for eligible dentists, discuss recruitment issues and enrollment progress, manage study documentation and procedures, and troubleshoot problems related to enrollment.

Dentists will be reimbursed \$75 for participation in the Stage 1 study. This is a cross-sectional questionnaire study; retention strategies are not applicable.

### 5.3.2 Stage 2 (Clinical Component)

The National Dental PBRN has demonstrated the ability to recruit practitioners and patients for clinical research studies. Since the clinical study is of short duration (approximately three weeks) and there is significant incentive to return (to receive a crown), patient retention is expected to be high. Regardless, the following procedures will be in place to ensure study retention:

- At the time of the crown preparation appointment, a crown insertion appointment will be made within approximately three weeks of the crown preparation appointment.
- If the patient has not returned to the office within four weeks of the crown insertion appointment, the Regional Administrative Site (RAS) will contact the office to investigate the cause of the delay and will work with the dental office to coordinate the follow-up appointment.

Dentists will be reimbursed \$50 for completion of the tooth preparation CRF and another \$25 at crown insertion for the completion of the crown insertion CRF. Dental Laboratory Technicians will be reimbursed \$25 for completion of the Laboratory Evaluation questionnaire. Enrolled patients will not receive any compensation for their participation in the study.

## **5.4 Practitioner and Patient Withdrawal**

### **5.4.1 *Reasons for Withdrawal***

Patients are free to withdraw from participation in the study at any time upon request.

### **5.4.2 *Handling of Practitioner and Patient Withdrawals***

Practitioner: Dentists who withdraw from the study will not be replaced.

Patients: Patients who withdraw from the study will not be replaced.

Laboratories: Laboratories who withdraw from the study will not be replaced.

## **5.5 Premature Termination or Suspension of Study**

This study may be suspended or prematurely terminated if there is sufficient reasonable cause. Written notification, documenting the reason for study suspension or termination, will be provided by the suspending or terminating party. If the study is prematurely terminated or suspended, the GPI will promptly inform the Institutional Review Board (IRB) and will provide the reason(s) for suspension or termination.

Circumstances that may warrant termination include, but are not limited to:

- Determination of unexpected, significant, or unacceptable risk to patients.
- Insufficient adherence to protocol requirements.
- Data that are not sufficiently complete and/or evaluable.
- Determination of futility. A power (sensitivity) analysis will be used to track whether loss to follow-up that will occur during the study jeopardizes the validity of the primary outcome measure.

## 6 STUDY SCHEDULE

### 6.1 Stage 1 Questionnaire Component: Enrollment/Baseline

- Eligible practitioners will be identified from responses to National Dental PBRN Enrollment Questionnaire and will be invited to complete an online or printed questionnaire over a period of three to four months.
- Completion of the questionnaire will indicate tacit consent.

### 6.2 Stage 2 Clinical Component: Pre-Enrollment/Screening

#### 6.2.1 Practitioner: Pre-Enrollment

- Practitioner and staff undergo training for the clinical component of the study.
- Practitioner will approach and confirm participation of his/her dental laboratory or laboratories.

#### 6.2.2 Patient: Screening

- Designated office personnel will introduce the study to the potential patient and will verify inclusion/exclusion criteria.

Informed consent, enrollment, examination, and treatment may occur during the same dental visit at which eligibility was confirmed.

#### 6.2.3 Laboratory: Pre-Enrollment

- Participating laboratory technician undergoes training for the clinical component of the study. Completion of the Laboratory Evaluation of Case questionnaire will be conducted.

### 6.3 Stage 2 Clinical Component: Enrollment/Baseline (Time: Day = 0)

#### 6.3.1 Patient: Enrollment

- Verify inclusion/exclusion criteria.
- Initiate consent procedures and document consent from the patient.
- Obtain demographic information on Patient Characteristics CRF.

#### 6.3.2 Practitioner: Baseline

- After the practitioner performs a crown preparation and impression appointment, the CRF "Crown Preparation" is completed by the practitioner for each patient. Practitioners send the crown impression and supporting materials to the lab(s) that have agreed to participate in the study.
- Practitioners using optical scanners (e.g. CEREC) along with a commercial lab and/or in-office milling will send the files to the independent laboratory for review.

## **6.4 Stage 2 Clinical Component: Laboratory Assessment**

### **6.4.1 Laboratory: Baseline**

- Upon receipt and assessment of the crown impression and supporting materials from the practitioner, the dental laboratory technician completes the “Laboratory Evaluation of Case” questionnaire.
- Completion of the questionnaire indicates tacit consent.
- Similarly, technicians at the independent laboratory will complete the questionnaire upon receipt and review of the digital files for practitioners using optical scanners (e.g. CEREC) along with a commercial lab and/or in-office milling.

## **6.5 Stage 2 Clinical Component: Final Study Visit (Time: Target Day 42)**

### **6.5.1 Practitioner: Final Study Visit**

- After the patient returns for the crown try-in appointment, and the crown is either inserted or rejected.
- The practitioner completes the CRF “Crown Insertion”.

## **6.6 Withdrawal**

If a patient decides to withdraw from the study, the date and reason for withdrawal will be recorded on the discontinuation CRF and submitted to the RAS.

## 7 STUDY PROCEDURES/EVALUATIONS

### 7.1 Stage 1 Questionnaire Development and Administration

#### Practitioner Questionnaire Development

This questionnaire was developed by our study team, which had input from dentists, laboratory technicians, and a statistician with content expertise in crown insertions. Following the development of the questionnaire, the instrument was reviewed and evaluated by Instrument Design, Evaluation, and Analysis (IDEA) Services at the CC, a group with expertise in questionnaire development and implementation.

#### Cognitive Interviewing

A pretest was given to eight dentists recruited from a list provided by the National Dental PBRN in the form of cognitive interviews conducted over the telephone. The interviews were conducted by IDEA Services at the CC. Nine practitioners were approached and eight interviews were conducted. General practitioners from five of the six National Dental PRBN regions participated, providing regionally balanced responses. Survey researchers believe that pretesting new surveys can have a substantial positive effect on data quality. During the interviews, respondents reviewed their responses to a completed questionnaire, and cognitive interviewers probed to assess possible respondent problems in understanding questions, recalling necessary information, and/or reporting accurately. We also asked participating dentists how relevant they think the items in the draft questionnaire were to issues of crown placement, and whether any issues relevant to crown placement were not addressed in the questionnaire. A paper version of the instrument was used during this assessment, because it provided an opportunity to observe if respondents had problems with instructions or any other language in the questionnaire. Results from the pretest resulted in appropriate questionnaire revisions.

#### Questionnaire Testing-Retesting

The online version of the questionnaire will be administered twice to a subset of approximately 30 to 40 practitioners to assess the test-retest reliability of the questionnaire. Practitioners who complete the online version of the initial questionnaire will be sent a second online questionnaire request by email approximately two weeks after receipt of the first completed questionnaire.

Practitioners will be randomly selected for the retest. The selection will be based on the response rate to the initial survey. Each practitioner will be given approximately one week to complete the retest. If the retest is not completed within the timeframe, the link to the retest questionnaire will be disabled. This process will be continued until 30 practitioners complete the retest. The questionnaire will take up to 30 minutes to complete each time.

#### Website and Questionnaire Pilot Testing

The CC's IT team will perform extensive internal testing of the website, including internet browser compatibility. Study team members (e.g., SPI, National Network Director (NND), Regional Directors, Statistician and Regional Coordinators (RC)) will also be given the opportunity to externally test the website prior to administration with study participants.

### Questionnaire Content

The questionnaire includes items to collect the date and assess the outcome measures specified in subsection 3.2. Some information will be collected from the National Dental PBRN Enrollment Questionnaire (e.g., demographics and practice characteristics) and linked to participants' responses to the study questionnaire.

Each practitioner's "clinical acceptability" level will be ranked using a vignette series within the questionnaire. Practitioners will be shown a series of clinical photographs and scenarios of crowns and impressions and asked to rate these as clinically acceptable or unacceptable. As an example, practitioners will be shown a picture of an impression with a small bleb or defect at the finish line, and asked if it is clinically acceptable. These rankings of practitioner exactness will help us interpret the results of the study.

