#### 3.2 Study Outcome Measures

##### 3.2.1 *Primary Outcomes*

To estimate the percentage of single-unit crowns deemed acceptable by the practitioner at clinical try-in, the practitioner rating of crown acceptability after being returned from the laboratory for clinical try-in will be ascertained in the Stage 2 portion of the study.

A concern of this outcome measure is that it is not standardized among practitioners. Some practitioners may be very exacting, rating one crown unacceptable that would be accepted by another practitioner. However, the decision about crown acceptability is an important outcome measure for this practice-based research study, regardless of the practitioner's technical ability or clinical bias. Further, each practitioner's "clinical acceptability" level will be ascertained using a question from the questionnaire administered during Stage 1 (before the clinical component) of the study (see Section 7) as well as data from the laboratory CRF analyzing the technical aspects of the crown preparation, impression and bite registration.

To identify factors associated with practitioner acceptability of crowns, the following practice/practitioner, patient/clinical, and prosthodontics technique variables will be ascertained via a Case Report Form (CRF) administered during the crown preparation and impression appointment (during Stage 2), while the practitioner factors will be obtained from the National Dental PBRN enrollment questionnaire:

- **Practice/practitioner factors** (percentage of practice time spent doing fixed prosthodontics; whether or not the practitioner has had prosthodontic, advanced general dentistry residency, or MAGD training; years in practice; network region);
- **Patient/clinical factors** (tooth position; corono-apical position of the crown preparation margin; dentist-assessed quality of hemostasis during the crown impression; endodontic status; whether the crown has proximal contacts; type of tooth opposing the crown); crown preparation design; and

- **Prosthodontic technique factors** (impression technique; impression material; whether the person making the impression is a dentist or a dental assistant; crown preparation design; dentist-assessed quality of the opposing cast and centric jaw relation; material used for the prosthetic crown).

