### Stage 2. Clinical study of crown fit.

A subset of 200 practitioners will be selected from practitioners who complete the practitioner questionnaire from Stage 1, based upon responses to the questionnaire items. Practitioners will be included from each of the network regions, and region will be included as a stratification variable in all statistical analyses. Data will be collected on practitioner gender, time since graduation, numbers of crowns done each month, remake rates, use of optical impression systems, group vs. solo practitioners, and insurance-based status of the practice. These will be evaluated for possible inclusion in multivariable statistical models for prediction of crown acceptability. Further, practitioners must do at least seven crowns per month to be eligible for the study, pending an adequate distribution of responses to the applicable question on the Stage 1 questionnaire. Each practitioner will be asked to report prospective data about patient/clinical factors during crown preparation and impression and crown insertion appointments and technical aspects of these appointments, with a goal of assessing 20 prepared teeth/crowns. We estimate that approximately 4000 prepared teeth/crowns will be evaluated in this Stage 2 portion of the study. Participating practitioners will be requested to enroll patients until they either 1) reach their enrollment goal of approximately 20 observations, 2) reach the end date for patient enrollment, or 3) decline further participation. They also must confirm the participation of their dental laboratory.

The clinical component is a longitudinal cohort analysis to find associations between practitioner characteristics, patient characteristics, and technical dental factors and crown acceptability rates. Practitioners will complete a case report form (CRF) at the time of tooth preparation, and again at crown insertion. Only single-unit crowns supported by a natural tooth are eligible. The length of participation for each patient will be approximately 3-6 weeks (i.e., the length of time between preparation and crown insertion).

Laboratory evaluation of crowns.

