### 11.3 Final Analysis Plan

**Primary objective:** (1) Estimate the percentage of single-unit crowns deemed acceptable by the practitioner at clinical try-in, and (2) identify factors associated with crown success.

The primary analysis for this aim will utilize generalized linear models to conduct logistic regression analysis, accounting for clustering of observations contributed by the same practitioner. A term representing the individual practitioner will be included as a random effect in the model. Estimation will be conducted using generalized estimating equations (GEE). The outcome variable will be dichotomous, indicating a crown being judged unacceptable by the practitioner.

Blocks of variables representing prosthodontic technique factors, patient/clinical factors and dentist factors will be evaluated as potential predictors of unacceptable crowns. These will be included as fixed effects in the model. Initial analysis will utilize separate models for each of the potential predictor variables. Multivariable models will be constructed using the variables found to be significant in each block and across blocks. These will be evaluated as predictive models for unacceptable crowns.

**Secondary objective:** (1) Quantify the prevalence of different methods and procedures utilized with crown preparations, and (2) explore whether these methods are significantly associated with dentist and practice characteristics.

The methods and procedures that will be included in the questionnaire are (1) crown preparation techniques; (2) impression techniques and impression materials; (3) materials used to fabricate crowns; (4) indications for recommending a single-unit crown restoration to a patient; and (5) the number of different dental laboratories to which the practitioners sends single-unit crowns to be fabricated.

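### The practitioner exactness score, the protocol's answer to an unstandardised primary outcome, is named in no predictor list and not in the primary model

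*Protocol*

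**What the plan says.** The primary outcome is the practitioner's own rating of the crown at try-in. Protocol 3.2.1 is open about its weakness: "A concern of this outcome measure is that it is not standardized among practitioners", and "Some practitioners may be very exacting, rating one crown unacceptable that would be accepted by another practitioner". It keeps the outcome because the decision matters in a practice-based study "regardless of the practitioner's technical ability or clinical bias". It adds that each practitioner's acceptability level will be measured in Stage 1, and that laboratory form data will be available.

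Section 7.1 (Questionnaire Content) describes the instrument: photographs and scenarios that the practitioner judges acceptable or not. Its stated purpose is: "These rankings of practitioner exactness will help us interpret the results of the study".

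The analysis text does not pick it up:

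- The practice/practitioner factors in 3.2.1 are time spent on fixed prosthodontics and a list of training routes ending "advanced general dentistry residency, or MAGD training; years in practice; network region".
- Section 4 (Stage 2) adds candidates: "Data will be collected on practitioner gender, time since graduation, numbers of crowns done each month, remake rates, use of optical impression systems", then group or solo practice and insurance status. Of these it says: "These will be evaluated for possible inclusion in multivariable statistical models for prediction of crown acceptability".
- Section 11.3 says: "Blocks of variables representing prosthodontic technique factors, patient/clinical factors and dentist factors will be evaluated as potential predictors of unacceptable crowns". A practitioner random effect is added, estimation is by GEE, and multivariable models are built from the significant variables.

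The exactness score is named in none of these places, and section 11 describes no adjusted, stratified or sensitivity analysis that uses it. The laboratory rating enters a model only for secondary objective (4).

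**The concern.** Primary objective (2) asks which factors are associated with crown success, and the Rationale (2.2) puts first the question whether impression technique changes the remake rate. If exacting practitioners prefer certain techniques or materials, the odds ratio for such a technique partly measures who rejects more crowns. A random effect or a working correlation allows for crowns from one practitioner being alike, but treats the practitioner's level as unrelated to the covariates. It therefore leaves this confounding in place. Selection by significance can then carry a spurious technique effect into the final model. The protocol has planned a direct measure of the confounder and does not say that it will be used for adjustment.

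**Working it through.** **Inputs from Protocol 11.2.** 200 dentists, 20 crowns each, 5% unacceptable, ICC 0 to 0.05, factor prevalence 50% in the unacceptable group, detectable odds ratio 1.78 at 80% power.

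**The plan's own figure.** Effective N = 4000 / (1 + 19 × 0.05) = 4000 / 1.95 = 2051, split 5%/95%. With the pooled chi-square test and two-sided alpha 0.05 (assumed; 11.2 states none), the detectable odds ratio is 1.765 and power at 1.78 is 81.1%. This agrees with the plan, and the point does not affect the sample size.

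**Inputs that are assumptions.** The documents give neither the spread of strictness nor its link to technique, so ranges are used. The technique has no true effect (odds ratio 1) throughout.

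**Two-group set-up.** Half the practitioners are strict. With a strict/lenient odds ratio of 3 and 5% overall, rejection is 7.4% and 2.6%. The implied ICC is 0.024² / (0.05 × 0.95) = 0.012, inside the protocol's range. If 70% of strict and 30% of lenient practitioners' crowns use the technique:

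- rejection with the technique = 0.7 × 7.4% + 0.3 × 2.6% = 5.96%
- rejection without it = 0.3 × 7.4% + 0.7 × 2.6% = 4.04%
- crude odds ratio = (0.0596/0.9404) / (0.0404/0.9596) = 1.51

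Exchangeable logistic GEE, 200 × 20, 150 runs per case. In each pair the technique is fixed per practitioner first, then varying by crown. Harm declared has a nominal rate of 2.5%.

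| Strict/lenient OR | Technique use | Mean OR, no score | Harm declared, no score | Mean OR, score in model |
|---|---|---|---|---|
| 3 | 50/50 | 1.02 / 0.99 | 4% / 3% | 1.02 / 0.99 |
| 3 | 60/40 | 1.24 / 1.21 | 27% / 24% | 1.01 / 1.02 |
| 2 | 70/30 | 1.32 / 1.31 | 43% / 50% | 1.01 / 1.02 |
| 3 | 70/30 | 1.50 / 1.42 | 73% / 65% | 0.99 / 0.99 |

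With 150 runs, a 5% rate has a standard error of √(0.05 × 0.95 / 150) = 1.8 points. A random-intercept logistic fit without the score (40 runs, odds ratio 3, 70/30) gave 1.57 and 1.40, against 1.56 and 1.39 for GEE in the same runs. The random effect does not cure the bias.

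**Continuous set-up.** Between-practitioner SD is 0.94 on the logit scale (ICC 0.05, the top of the protocol's range). Strictness explains 25% to 50% of that variance, and the odds of technique use rise 1.65 to 2.7 times per SD of strictness. Four cases, 150 runs each:

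- without the score: mean OR 1.13, 1.18, 1.24, 1.33; false positives 11%, 19%, 33%, 52%
- with a perfectly measured score: 1.01, 1.01, 1.00, 0.99; false positives 4%, 3%, 6%, 5%

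**Imperfect score.** In the same kind of set-up (120 runs per case), a score with reliability 0.6 left mean OR 1.06 to 1.17 and false positives of 7% to 22%. Adding the practitioner's mean technique use brought these to 1.00 to 1.01 and 4%. For a technique that varies within a practitioner, the mean alone, without the score, gave 0.99 to 1.01 (100 runs per case).

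**The case against.** Several replies have weight.

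- **The model is not closed.** A reader might infer that the score is excluded from the primary model. The text does not say so: dentist factors in 11.3 is an open category, and helping interpretation does not rule out modelling. What stands is that the score is not named. That is more than a detail left to a later plan, because the protocol itself lists the candidate covariates and sets the model and selection rule.
- **There is a partial proxy.** Remake rates, a candidate in section 4, come close to measuring rejection tendency. With a rate assumed to rest on 84 earlier crowns (seven a month for a year), adjustment cut mean OR from 1.11 to 1.35 down to 1.05 to 1.17, and false positives from 6% to 54% down to 3% to 17%. This helps but is incomplete, and inclusion is only possible, not planned. The figures without the score are thus a worst case with no practitioner covariate.
- **The outcome was chosen knowingly.** Accepting the decision whatever the practitioner's bias is a sound defence of estimating the percentage acceptable. It does not defend attributing differences in rejection to technique.
- **The score may be missing.** Stage 2 entry requires completing Stage 1 (5.1.2), so one might infer that every Stage 2 practitioner has a score. Section 2.3.1 lets practitioners skip questions, so some may not.
- **The size is conditional.** With a smaller spread (SD 0.5), the mildest continuous case gave about 6% false positives, close to nominal.

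**Conclusion.** The point holds in a limited form. The protocol names the problem, plans a measure of it, and does not carry that measure into the predictor lists or the primary model; the practitioner random effect and GEE do not replace it. If strictness and technique choice are related, technique odds ratios are biased. Under the assumed links a neutral technique showed mean odds ratios of about 1.1 to 1.5, with false-positive rates from slightly to heavily inflated.

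It would go too far to conclude that the technique results will be biased, or biased towards harm. The documents give no figure for the link, none of the bias appears without it, and the opposite link would make a neutral technique look protective or hide a harmful one. The return to odds ratios near 1 assumes a score measured without error; a noisy score removes only part of the bias.

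**What to change.** In Protocol 11.3:

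1. Name the Stage 1 exactness score as a prespecified dentist-level covariate, kept in the multivariable primary model regardless of significance. Define how it is derived from the vignette items.
2. Add a missing-score category, so that practitioners who skipped the vignettes, with about 20 crowns each, are not dropped.
3. Report technique odds ratios with and without the score.
4. For technique factors that vary within a practitioner, add the practitioner's mean of the factor, at least as a sensitivity analysis, to separate within- from between-practitioner effects. This cannot help for a technique that a practitioner always or never uses; there the score is the main protection.

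Cost: no new data. The score takes one or two degrees of freedom. The means take more: if Stage 2 uses the category counts that 11.3 expects for Stage 1 (three impression techniques, three impression materials, five crown materials), that is 2 + 2 + 4 = 8 terms before the other technique factors, against about 4000 × 5% = 200 unacceptable crowns. That is the reason to allow the means as a sensitivity analysis.
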